In a local study, more than 30% of type A aortic dissection (TAAD) patients were misdiagnosed in the ED. Among these misdiagnosed patients, many presented with normal blood pressure and relatively mild signs and symptoms, resulting in their triage in lower categories.(9) Additionally, the absence of a POCUS ultrasound exam was identified as an

independent factor associated with misdiagnosis in the ED.(9) Therefore, performing a POCUS scan could help identify TAA and TAAD patients in the ED even when they have a low pretest probability.

Aim

This study aims to evaluate the prevalence of TAA in hypertensive patients identified in the ED using POCUS.

Objectives

- 1. To investigate the number of hypertensive patients presenting to the ED with a rtic diameter \geq 4.5 cm as indicated by POCUS
- 2. To evaluate the number of patients with confirmed TAA as verified by CTA
- 3. To evaluate the agreement of aortic diameter measurement between CTA and POCUS

Hypotheses

1. POCUS can identify TAA by measuring the aortic diameter.

Methodology

This prospective cohort study is coordinated by the Accident and Emergency Medicine Academic Unit of the Chinese University of Hong Kong (CUHK) in collaboration with the Department of Surgery and the Department of Medicine and Therapeutics of CUHK. The investigators will carry out this study in the accident and emergency department at Prince of Wales Hospital (PWH). PWH serves a population of 1.6 million people in the New Territories of Hong Kong and is the main teaching hospital of CUHK. The investigators will be trained for POCUS before the commencement of the study and the images will be audited by an echocardiologist.

Inclusion and exclusion criteria for participants

Inclusion criteria:

- 1. Adult patients aged \geq 18 years attending the ED during the study period
- 2. Known history of hypertension or newly diagnosed hypertension in the ED

Exclusion criteria:

- 1. Known history of aortic aneurysm or dissection
- 2. Previous thoracic aortic interventions or endovascular stenting
- 3. Patients in cardiopulmonary resuscitation

- 4. Traumatic patients
- 5. Patients refuse to participate the study

Sample size calculation

According to previous studies, the estimated prevalence of TAA in hypertensive patients in a clinic was 7.5% and the area under the curve for POCUS detecting aortic dilation was 0.857.(5, 10) With a confidence level of 95% and margin of error of 5%, 1186 patients will be needed.(11)

To ensure that this study has enough participants after accounting for a 20% inadequate visualization of the POCUS image, the investigators will need to recruit 1483 participants. The investigators target to complete the recruitment within 12 months.

Data collection

The investigators trained with POCUS will recruit and screen patients in the ED during the study period using an ultrasound device throughout the study and all images will be stored for regular review by an echocardiologist.

POCUS screening will be conducted to measure the maximum diameters at end diastole of the aortic root, ascending aorta, aortic arch, and descending thoracic aorta. The internal diameter will be measured perpendicular to the axis of blood flow and leading edge to leading edge in accordance with the guidelines set forth by the American College of Cardiology.(12) Measurements of the aortic root and ascending aorta will be taken using parasternal long-axis views, while the aortic arch will be assessed from the suprasternal view. The descending thoracic aorta will be examined using modified apical 2-chamber and subcostal views. The investigators will also specifically look for an intimal flap, pericardial effusion and aortic regurgitation.

The investigators will inform the emergency physicians under the following conditions:

- 1. patient has an aortic diameter \geq 5cm
- 2. patient has an intimal flap, pericardial effusion or moderate aortic regurgitation

If physicians identify a clinical possibility of TAA, these patients will be referred to cardiothoracic surgeons. If there is a suspicion of acute aortic syndrome, the ED physicians will consult cardiothoracic surgeon urgently \pm CTA in the ED as usual practice.

Relevant clinical data (such as past medical history, laboratory results, operation records etc.) will also be collected. In addition, the investigators will follow up with the patients for 28 days to monitor mortality and any advanced imaging performed outside the ED.

Outcome measurement

The primary outcome is the number of patients with TAA (a maximum aortic diameter of \geq 4.5 cm and/or \geq 50% localized enlarged diameter relative to the adjacent normal segment as indicated by POCUS).

The secondary outcomes include the number of patients with confirmed TAA as verified by CTA, BMI for all participants, the number of CTA scans conducted for TAA confirmation, the number of surgical interventions performed among TAA patients, the ICU admission rate, ICU length of stay, hospital length of stay and mortality, proportion of adequate visualisation of POCUS studies obtained, agreement of aortic diameter measurement between CTA and POCUS, and signs and symptoms of TAA patients presenting to the ED. In addition, the investigators will assess the 28-day all-cause mortality and any advanced imaging done outside the ED for evaluating the aorta.

Statistical analysis

Patients with a maximum aortic diameter ≥ 4.5 cm and/or $\geq 50\%$ localized enlarged diameter relative to the adjacent normal segment are regarded as TAA while those with an aortic diameter < 4.5 cm are regarded as non-TAA. Comparison of baseline characteristics and aortic size measurements will be made between these two groups of patients. Categorical variables will be compared with Chi square test or Fisher's exact test. Continuous variables will be compared using Student's t-test or Mann-Whitney U test, based on the results of the Shapiro-Wilk W test. Binary logistic regression analysis will be used to identify the risk factors that associated with TAA independently and to predict the presence of TAA. Variables with a p < 0.2 from the univariate analysis will be included in the stepwise logistic regression model. In patients who underwent a CTA, the investigators will assess the agreement of aortic diameter measurements between CTA and POCUS using Bland-Altman analysis. All statistical analyses and visualisations will be done using R or Prism GraphPad.(13, 14) A significance level of 0.05 will be considered statistically significant.

Patients with missing data on certain variables will be removed from that particular analysis. POCUS studies with inadequate visualisation of all views will be discarded.

Ethics

All participants will provide written informed consent. Patients' relatives can provide consent if the patient is not mentally capable of doing so. If no relatives are present in the ED, the investigators will obtain deferred consent as soon as the patient is awake. If the patient passes away before they can consent to this study, all images and data collected will be discarded. No images and data will be used without consent. Participants are allowed to withdraw from the study at any time during the study period and their data will be discarded. This study will be conducted in full compliance with the Declaration of Helsinki and the principles of Good Clinical Practice. The investigators will seek ethical approval from our local review committee.

Funding and Sponsor

There is no funding or sponsorship for this study.

Potential Conflicts of Interest

The PI and CI have declared no potential conflicts of interest.

Safety Management

Ultrasound is a safe screening tool and does not cause any adverse effects to patients. Any incidental findings of aortic abnormalities will be reported to the attending physician. The investigators will abort the POCUS scan immediately and inform the attending physician in the event of any deterioration. Necessary resuscitation will be initiated without further delay.

Cost and Benefit for Participants

There is no additional charge or reward for participation in this study.

Confidentiality and privacy

Ultrasound images will be stored in both the device and the CUHK internal drive. All clinical data will be collected using the CU WebForm and will be kept confidential. Data will be destroyed 7 years after the publication of the study. Signed consent forms will be saved in a locked cabinet in the research office.

References

4. Digital Policy Office. Inpatient Discharges and Deaths in All Hospitals Classified by Disease for the Year 2022 (English). https://data.gov.hk/en-data/dataset/hk-dh-dh_ncddhss-ncdd-dataset-102022.

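### The 50% relative-enlargement limb of the primary outcome needs a reference diameter that the protocol neither defines nor lists for measurement

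*Protocol*

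**What the plan says.** The protocol's Outcome measurement section gives the primary outcome two limbs joined by and/or. One is a maximum aortic diameter of at least 4.5 cm. The other is an enlargement of at least 50%, described as localized and judged against a neighbouring normal part of the aorta: "enlarged diameter relative to the adjacent normal segment as indicated by POCUS". Statistical analysis repeats the rule for grouping patients: those at or above 4.5 cm and/or with a 50% "localized enlarged diameter relative to the adjacent normal segment are regarded as TAA". The comparison group is set by absolute diameter alone: "while those with an aortic diameter < 4.5 cm are regarded as non-TAA".

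Data collection says what is measured. POCUS will "measure the maximum diameters at end diastole of the aortic root, ascending aorta, aortic arch, and descending thoracic aorta". The root and ascending aorta share the parasternal long-axis view. By contrast, "the aortic arch will be assessed from the suprasternal view", and the descending aorta is examined from modified apical 2-chamber and subcostal views. On storage, "all images will be stored for regular review by an echocardiologist". On image quality, "POCUS studies with inadequate visualisation of all views will be discarded".

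Objective 1 counts only patients at or above 4.5 cm and does not mention the relative limb.

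**The concern.** Either limb alone is sufficient, so the relative limb can by itself make a patient a primary-outcome case. It needs a numerator (the enlarged diameter) and a denominator (the adjacent normal diameter). Only maxima are listed. The protocol does not define what counts as adjacent, normal or localized, and does not say whether the comparison is made within a segment or between named segments.

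Two operators following the text could therefore classify the same patient differently. The limb feeds the primary count, the TAA versus non-TAA comparison and the logistic regression for TAA, so any inconsistency carries through to all three. A statistical analysis plan could define the ratio later, but it cannot supply a diameter that nobody planned to take.

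**Working it through.** **1. The plan's own figures.** Inputs from Sample size calculation: AUC A = 0.857, prevalence 7.5%, 95% confidence, margin 5%. The Hanley-McNeil standard error uses Q1 = A/(2 − A) = 0.7498 and Q2 = 2A²/(1 + A) = 0.7910. With N = 1186 the confidence-interval half-width is 1.96 × 0.0255 = 0.04998, so 1186 reproduces. Then 1186/0.8 = 1482.5, rounded up to 1483, which also reproduces. The point below does not alter the sample size.

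Expected cases are 0.075 × 1186 ≈ 89. The half-width for the prevalence itself is 1.96 × √(0.075 × 0.925/1186) = 0.015, or 1.5 percentage points.

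**2. What the listed data allow.**

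| Reading of the relative limb | Needed | Listed |
|---|---|---|
| Bulge beside normal aorta in the same segment | Two diameters in one segment | One maximum per segment |
| One named segment against its neighbour | Both segments' maxima | Yes, if both were seen; apart from root and ascending aorta, the views differ |

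Under the first reading, a descending aorta of 3.9 cm beside 2.5 cm has a ratio of 3.9/2.5 = 1.56 and meets the criterion, but the list records only 3.9 cm. Under the second, an ascending maximum of 3.6 cm and an arch maximum of 2.4 cm give 3.6/2.4 = 1.5 and meet the criterion with no bulge. A study is discarded only when all views are inadequate, so a retained patient may lack the neighbouring value.

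**3. Where the limb adds cases.** A case below 4.5 cm requires 1.5 × reference < 4.5, so the reference must be under 3.0 cm. A reference of 2.8 cm gives a threshold of 4.2 cm, and 2.4 cm gives 3.6 cm.

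**4. Size if neighbouring maxima were used.** The documents give no normal diameters, so every input here is an assumption:
- mean diameters: root 3.5–3.6, ascending 3.4–3.5, arch 2.7–3.0, descending 2.3–2.5 cm;
- common SD 0.3–0.4 cm, between-segment correlation 0.3–0.7, multivariate normal.

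The quantity simulated is the share of these aneurysm-free patients with all four diameters below 4.5 cm and at least one immediate-neighbour ratio of 1.5 or more.

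| Means (cm) | SD | Correlation | Share |
|---|---|---|---|
| 3.5/3.4/2.9/2.5 | 0.3 | 0.7 | 0.6% (lowest) |
| 3.5/3.4/2.9/2.5 | 0.3 | 0.5 | 2.4% |
| 3.5/3.4/2.9/2.5 | 0.4 | 0.5 | 9.1% |
| 3.5/3.5/2.7/2.3 | 0.4 | 0.3 | 29% (highest) |

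Applied to the 92.5% without TAA, this adds 0.006 × 92.5 ≈ 0.6 to 0.29 × 92.5 ≈ 27 percentage points to a prevalence of 7.5%. A slightly different set of assumed means, with measurement error of up to 0.2 cm added, gave about 1% to 39%.

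The mean ratios of immediate neighbours within these ranges stay between about 1.0 and 1.3 (for example 3.0/2.3 = 1.30), below 1.5. The mislabelled patients come from the tails of the distribution.

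**5. Group definitions.** Take a patient with a largest diameter of 3.9 cm and a reference of 2.5 cm. The relative limb places this patient in TAA, and the diameter below 4.5 cm places the same patient in non-TAA. Statistical analysis as worded assigns the patient to both groups.

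**The case against.** The strongest reply is that the protocol nowhere says one segment's maximum will be divided by the next. The words localized and normal point to a focal bulge beside healthy aorta, which is not the same as taper. Trained operators look at the image and can see a bulge. Images are stored and reviewed by an echocardiologist, so a reference diameter could be read afterwards, and the data form, which is not shown, might already have a field for it.

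Much of this stands. A reader might infer that the protocol will label normal taper as TAA, or that a bulge within one segment cannot be recognised. The text supports neither: the cross-segment rule is one possible reading, average taper under the assumed values does not reach 50%, and a bulge can be seen even if its ratio is not recorded. It would also be too strong to say that no comparator exists, since neighbouring maxima are collected and images are kept.

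The reply does not remove the gap. Seeing a bulge does not establish that it exceeds 50%; that needs a second measurement, and none is listed. The stated purpose of keeping the images is review, and no reference reading from them is planned. Reading localized as within-segment makes the listed data insufficient for the ratio.

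**Conclusion.** The point holds in a limited form. A sufficient limb of the primary outcome rests on a reference diameter that is neither defined nor in the measurement list, so it cannot be applied reproducibly as written. From the listed data it is either not computable or computable only across neighbouring segments, where some normal taper could be counted as TAA.

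The documents do not fix the size. About 0.6% to 29% of aneurysm-free patients would be labelled under the assumed diameters, SDs and correlations, and only if neighbouring maxima were used. At the low end the effect is smaller than the 1.5-point half-width of the prevalence estimate; at the high end it exceeds the expected 7.5% several times over. A reader might want a single number of false cases, or might infer that small arch or descending diameters would emerge as risk factors. The documents support neither: the number depends wholly on assumptions, and the protocol does not name diameters as predictors in the logistic model.

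Two related inconsistencies need no outside data. A patient below 4.5 cm who meets the relative limb falls in both analysis groups, and Objective 1 uses only the 4.5 cm limb. The sample size is unaffected. This should be corrected before recruitment.

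**What to change.** - **Data collection:** when a localized enlargement is seen, record a reference diameter of the adjacent normal-calibre aorta in the same anatomical segment and the same view, from the live or the stored image. Compute the 50% criterion only from that pair, so that maxima of different named segments are not compared.
- **Outcome measurement:** refer to that pair in the definition. Report patients who meet only the relative limb on a separate line beside the count at or above 4.5 cm, so that the result can be read against Objective 1.
- **Statistical analysis:** define non-TAA as meeting neither limb.

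The cost is one extra caliper reading in the few patients with a suspected bulge, one form field and a few sentences. The change does not remove dependence on the operator, who still has to notice the bulge, but it makes the classification checkable once one has been noticed.

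### POCUS diameters are significance-tested between groups they define, and the p < 0.2 entry rule, read literally, makes them eligible predictors in the TAA model

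*Protocol*

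**What the plan says.** All of this is in the protocol, mostly under Statistical analysis.

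- **Groups.** The TAA group is "Patients with a maximum aortic diameter ≥ 4.5 cm and/or" a local enlargement of at least 50% over the adjacent normal segment. For the other group, "those with an aortic diameter < 4.5 cm are regarded as non-TAA". Under Outcome measurement, the same definition is tied to POCUS.
- **What is compared.** "Comparison of baseline characteristics and aortic size measurements will be made between these two groups of patients".
- **How.** "Continuous variables will be compared using Student's t-test or Mann-Whitney U test", the choice depending on a normality test, and "A significance level of 0.05 will be considered statistically significant".
- **Model.** Binary logistic regression is to "identify the risk factors that associated with TAA independently and to predict the presence of TAA". The entry rule is: "Variables with a p < 0.2 from the univariate analysis will be included in the stepwise logistic regression model".
- **What is measured.** Under Data collection, the scan records "maximum diameters at end diastole of the aortic root, ascending aorta, aortic arch, and descending thoracic aorta".

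The group comparisons are the only univariate analysis described. Nothing in the section removes aortic diameters from the variables to which the entry rule applies.

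**The concern.** The segment diameters are the raw material of the outcome: the largest of them is cut at 4.5 cm, and the ratio criterion is also computed from diameters. A difference in diameter between the groups is therefore produced by the definition. Testing it answers no question.

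The second step matters more. A mechanical p < 0.2 screen will pass variables that differ by construction. Applied as written, it makes components of the outcome eligible as predictors of that outcome. A model containing them describes how the outcome was coded. It does not show which patient characteristics go with TAA, so its stated purpose of finding independent risk factors and predicting TAA would fail. This is distinct from the usual reservations about stepwise selection.

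**Working it through.** **1. The plan's own figure.** Inputs from Sample size calculation: AUC A = 0.857, prevalence 7.5%, 95% confidence, margin 0.05. The check uses the Hanley-McNeil variance, [A(1−A) + (n1−1)(Q1−A²) + (n0−1)(Q2−A²)]/(n1·n0), where Q1 = A/(2−A) = 0.7498 and Q2 = 2A²/(1+A) = 0.7910.

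With N = 1186, n1 = 1186 × 0.075 = 88.95 and n0 = 1097.05:
- numerator = 0.1226 + 87.95 × 0.01533 + 1096.05 × 0.05656 ≈ 63.46
- SE = √(63.46/97,583) = 0.0255
- half-width = 1.96 × 0.0255 = 0.04998

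The stated 1186 is reproduced, and 1186/0.8 = 1482.5 rounds up to 1483. The present point changes neither figure. The calculation does show that about 89 TAA cases are expected.

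**2. The logic, without simulation.** Write D for the set of segment diameters (and the ratios formed from them), X for patient characteristics, and Y for TAA. Y is a fixed function of D, so P(Y = 1 | D, X) is 0 or 1 whatever X is. Once D is fully known, X can add nothing. If the maximum diameter alone is entered and no patient is positive on the ratio alone, 4.5 cm separates the groups completely and no finite maximum-likelihood estimate exists.

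**3. Size if all four diameters enter.** The protocol gives no effect sizes, so these are assumptions:
- n = 1186, with 200 datasets per setting
- segment SDs of 0.45, 0.45, 0.35 and 0.30 cm for root, ascending, arch and descending
- age shifts each diameter by 0.35 of these units per SD of age, and male sex by 0.6
- residual correlation between segments of 0.3, 0.6 or 0.8
- TAA is a maximum of at least 4.5 cm, set at 7.5% prevalence; the ratio criterion is not simulated

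| Residual correlation | All four diameters p < 0.2 | Without diameters: OR age / male | Significant | With four diameters: OR age / male | Significant |
|---|---|---|---|---|---|
| 0.3 | 100% of runs | 2.13 / 3.93 | 100% / 100% | 1.01 / 1.04 | 5.5% / 5.5% |
| 0.6 | 100% | 2.03 / 3.92 | 100% / 100% | 1.01 / 1.10 | 4% / 7% |
| 0.8 | 100% | 2.00 / 3.61 | 100% / 100% | 0.99 / 1.08 | 5% / 6% |

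ORs are medians; age is per SD. With the diameters included, the significance rates are about the 5% false-positive rate. The maximum diameter separated the groups perfectly in every run.

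**4. Size if only some segments enter.** Two other sets of assumptions show how much this varies.
- Outcome built from root and ascending diameters only, with root alone entered: age significant in 13% of runs and sex in 5%.
- Residual correlation 0.5, smaller arch and descending diameters, TAA about 4.5%: root alone (AUC 0.95) left age significant in 49-60% of runs. Arch and descending together (AUC 0.64-0.81 each) left age significant in 99.5-100% (OR about 2.8-3.8) and sex in 63-91%.

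**5. What was not simulated.** The p < 0.2 screen was checked for the four diameters in step 3. No run carried out the stepwise selection, so these figures describe models with given diameters in them, not the full planned procedure.

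**The case against.** The strongest reply is that no sentence says diameters will go into the model. The model is for risk factors, and diameter is the definition of TAA, not a risk factor for it. An ordinary reader may picture a descriptive table followed by a model of patient characteristics, with the candidate list left to a statistical analysis plan. This stands in part: a reader might infer that the protocol commits to entering the outcome as its own predictor, and the text does not support that. But the point is more than a missing list. The protocol itself fixes an entry rule covering all variables from a univariate analysis that explicitly includes aortic size, and read literally that rule misfires.

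Other replies:

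- *Reporting diameters by group is useful.* Agreed; only the significance test is empty. CTA diameters might also be meant, and they do not define the outcome, so the point is confined to POCUS diameters and ratios.
- *The loss of association is built into the simulation.* It is, since age and sex act only through diameter there. For an outcome that is a cut of diameter this is also how they must act. The amount of loss still depends on which segments enter and on the assumed correlations, so it cannot be said that any one segment would erase the risk factors.
- *Separation may be incomplete.* Correct: a patient positive on the ratio alone can have a maximum below 4.5 cm. Separation on the maximum would then be near-complete. Non-convergence or extreme estimates would probably be noticed; single segments entering would be less conspicuous.
- *The model is peripheral.* It appears in neither the aim, the objectives nor the listed outcomes. This stands and limits the weight of the point. Nor is deciding whom to screen a stated purpose of the model.

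**Conclusion.** The point holds in a limited form. Testing POCUS diameters between groups cut on those diameters is circular on the face of the text, and this needs no assumption about intent. That the same diameters are eligible for the logistic model follows from the literal entry rule; whether they would be entered is not stated.

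If all the defining diameters enter, associations that act through diameter vanish, with odds ratios near 1 and significance at about the false-positive rate under every correlation tried. If only some enter, the loss ranges from slight to severe. The direction follows from the definition of TAA; the amounts rest on assumed effects and correlations and on models fitted without stepwise selection.

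A reader might infer that the study's main result is compromised. It is not: the count of TAA patients, the Bland-Altman agreement analysis and the sample size of 1186 (1483 recruited) do not depend on this. Only the group comparison and the risk-factor and prediction model are affected.

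**What to change.** Add one sentence under Statistical analysis, for example: POCUS aortic diameters and ratios that define TAA will be summarised by group descriptively, without significance tests, and will not be candidate variables for the logistic model.

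The exclusion should stop there. Limiting candidates to characteristics known before the scan would also bar findings such as aortic regurgitation or pericardial effusion, and possibly laboratory results. None of these defines TAA, and this point gives no reason to exclude them.

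The cost is one sentence. No data, patients or change to the sample size are needed.

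### Choosing Student's t-test or Mann-Whitney by a Shapiro-Wilk result leaves comparisons of about 89 with 1097 patients unprotected if the two groups differ in spread; Welch's test would be a cheap improvement

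*Protocol*

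**What the plan says.** The Statistical analysis section of the protocol divides patients into TAA and non-TAA by POCUS and states: "Comparison of baseline characteristics and aortic size measurements will be made between these two groups of patients". The rule for continuous variables is explicit: Student's t-test or "Mann-Whitney U test, based on the results of the Shapiro-Wilk W test". It does not say whether normality is tested within each group or on the pooled data, or at what level.

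The section then turns to the risk-factor model: "Variables with a p < 0.2 from the univariate analysis will be included in the stepwise logistic regression model". It does not say whether those p-values are the two-group tests just described or univariate logistic regressions. The overall threshold is given as "A significance level of 0.05 will be considered statistically significant".

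Group sizes follow from the Sample size calculation section, which assumes a TAA prevalence of 7.5% and states: "With a confidence level of 95% and margin of error of 5%, 1186 patients will be needed".

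**The concern.** With one group about twelve times the other, mild non-normality does little harm to a t-test, but unequal spread can do a lot. Student's pooled SD is then almost entirely the SD of the large group, while the uncertainty of the difference comes almost entirely from the small group. The Shapiro-Wilk step does not look at spread, so it does not guard against this.

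The step also responds strongly to sample size. At a skewness of 0.3 it rejects in about 96% of samples of 1097 but in only 17-19% of samples of 89. Where it rejects, the comparison moves from means to ranks, so different variables in one table may answer different questions.

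At stake are the error rates of the baseline comparisons at 0.05 and, on one reading of the text, entry of variables into the stepwise model at 0.2.

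**Working it through.** **Inputs.** From the protocol: prevalence 7.5%, AUC 0.857, 95% confidence, margin 5%, 1186 evaluable patients, 20% inflation, thresholds 0.05 and 0.2. Assumed, because the protocol gives no SD: TAA:non-TAA SD ratio r from 0.67 to 2, two-sided tests, Shapiro-Wilk at 0.05.

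**1. The protocol's own figures.** The protocol names no formula, but the Hanley-McNeil standard error of an AUC reproduces its number. With A = 0.857, Q₁ = A/(2−A) = 0.7498 and Q₂ = 2A²/(1+A) = 0.7910:

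SE² = [A(1−A) + (n₁−1)(Q₁−A²) + (n₀−1)(Q₂−A²)]/(n₁n₀)

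At N = 1186 the half-width 1.96·SE is 0.04998, and 1186 is the smallest N with a half-width of at most 0.05. Inflation: 1186/0.8 = 1482.5, so 1483. Both stated figures are reproduced.

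**2. Group sizes.** 1186 × 0.075 = 88.95 and 1186 × 0.925 = 1097.05, so about 89 and 1097, a ratio of about 1:12.

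**3. Why Student's test fails under unequal spread.** Set the non-TAA SD to 1.

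- Variance the test assumes: s²ₚ(1/89 + 1/1097), with s²ₚ = (88r² + 1096)/1184
- True variance of the difference: r²/89 + 1/1097

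For r = 1.5, s²ₚ = 1.0929, the assumed variance is 0.01328 and the true variance is 0.02619. The SE is too small by a factor √(0.01328/0.02619) = 0.712. The effective cut-off is 1.96 × 0.712 = 1.395, and a two-sided normal tail beyond 1.395 is 16.3%.

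**4. The protocol's rule, normal data, equal means.** The simulation used 4000 replicates per row, 89 v 1097. The rule was Mann-Whitney if Shapiro-Wilk rejects, otherwise Student's t. The second column is the formula in step 3; the rest are simulated.

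| SD ratio r | Student, formula, 5% | Rule, per-group pretest, 5% | same, 20% | Rule, pooled pretest, 5% | Welch, 5% | Welch, 20% |
|---|---|---|---|---|---|---|
| 0.67 | 0.6% | 0.9% | 8.1% | 0.8% | 5.2% | 20.7% |
| 0.8 | 1.8% | 2.1% | 12.4% | 1.8% | 5.7% | 20.1% |
| 1 | 5.0% | 5.1% | 20.5% | 5.1% | 5.3% | 20.3% |
| 1.25 | 10.5% | 10.3% | 29.4% | 9.9% | 4.7% | 20.2% |
| 1.5 | 16.3% | 15.8% | 36.1% | 13.1% | 4.6% | 19.6% |
| 2 | 26.5% | 25.3% | 45.1% | 13.4% | 5.1% | 19.9% |

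Student's t simulated with no pretest gives 10.2%, 16.3% and 26.3% at ratios 1.25, 1.5 and 2, almost the same as the per-group rule. Keeping the per-group pretest but using Welch in place of Student gives 4.8-6.0%. With normal data, then, the equal-variance test is the main cause.

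**5. Mild skew (0.3 in both groups), equal means.** The per-group rule sends 96-97% of samples to Mann-Whitney. Rejection at nominal 5% is about 2%, 8%, 11% and 15-16% at ratios 0.67, 1.25, 1.5 and 2. Welch without a pretest stays at about 5%. Here the pretest does matter: it replaces a comparison of means by one of ranks, and Mann-Whitney is not a valid test of equal means when spreads differ.

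**6. Equal distributions.** With the same distribution in both groups (normal, gamma or lognormal) the rule rejects in 4.4-5.6% at nominal 5% and 19.6-21.4% at nominal 20%.

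**7. The p<0.2 screen under the other reading.** If the screen uses univariate logistic regression, its likelihood-ratio test in the same normal scenarios rejects in 10.7%, 17% and 27% at nominal 5%, and 28%, 36% and 47% at nominal 20%, for ratios 1.25, 1.5 and 2. Changing the t-test would not alter those figures.

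**The case against.** The strongest reply has five parts.

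- **Error rates are not wrong as such.** A reader might infer that the rule fails in general. It does not: with equal distributions it is near nominal (step 6), and at a ratio of 1.1 the rejection rate is only about 6.4%. The protocol gives no SDs, and nothing in it points to a doubled SD. This stands, so the point is conditional.
- **The pretest is not the main culprit.** A reader might blame the Shapiro-Wilk step for the whole distortion. With normal data, Student's test alone does as badly. Many real variables would go to Mann-Whitney, where the distortion is smaller, and a pooled pretest also lowers the upper end. This stands for the highest figures. It does not remove the problem, since 8-16% remains with mild skew at ratios 1.25-2.
- **The feed into the model is an inference.** It is tempting to say that these p-values decide which variables enter the stepwise model. The text does not say so, and univariate logistic regression is an equally natural reading. This stands.
- **The stakes are low.** The primary outcome is a count, and agreement is assessed by Bland-Altman. The groups are defined by diameter, so a difference in aortic size is built in and its type I error hardly matters. A screen at 0.2 is permissive on purpose. All of this stands and limits the point to a minor one.
- **The choice of t-test could be left to an analysis plan.** This does not stand: the protocol has itself fixed both the tests and the rule for choosing between them.

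**Conclusion.** The point holds in conditional form, as a cheap improvement. The protocol fixes an equal-variance t-test or a rank test, chosen by a check that ignores spread, for groups of about 89 and 1097. If the TAA group's SD is 0.67 to 2 times the other group's (an assumed range), equal means are rejected at nominal 5% in about 1% to 25% of samples with normal data and about 2% to 16% with skewness 0.3. The upper figure for normal data depends on testing normality per group; a pooled pretest gives about 13%. Welch's test holds about 5% throughout these scenarios.

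The documents do not support saying that the error rates are wrong whatever the spread, that the pretest alone is responsible, or that these p-values certainly feed the model. The primary prevalence count and the Bland-Altman analysis are untouched.

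**What to change.** In the Statistical analysis section:

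1. Replace the Shapiro-Wilk selection rule and Student's t-test with Welch's t-test for continuous variables.
2. Name clearly skewed variables in advance for analysis on the log scale or by Mann-Whitney.
3. Report differences with 95% confidence intervals.
4. State whether the p-values for the p<0.2 screen come from these two-group tests or from univariate logistic regression. Welch's test corrects the screen only in the first case.

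The cost is two or three sentences. Design and sample size do not change, and both R and Prism offer Welch's test. The loss of power is negligible if variances are equal. Welch's test is somewhat liberal for strongly skewed variables left untransformed: 8.0% at nominal 5% for identical lognormal data with log-SD 1. Step 2 deals with that. Mann-Whitney results for the named variables should be described as comparisons of distributions, not of means.
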